7.1.6. Radiation Therapy Quality Assurance Review

NOTE: PRIOR TO DELIVERING ANY PROTOCOL TREATMENT, all WBRT-SIB treatment plans must be reviewed and approved by the Principal Investigator. WBRT-SIB treatment cannot be initiated until permission has been granted.

1. The Principal Investigator, [name], will perform an RT Quality Assurance Review for each case from all sites before the start of treatment. Plans should include complete data, including the fused planning MRI-planning CT image set with the associated treatment plan with dose-volume histogram (most often in the DICOM-RT format). Plans must be approved by the Principal Investigator prior to treatment initiation.
2. Acceptable Variations
 - a. Plans with up to 5% deviation in the specified dosimetric parameters in sections 7.1.1 and 7.1.7 may be approved by the Principal Investigator at his discretion.
3. Review Process and Unacceptable Deviations

Treating physicians may be required to modify MRI-CT fusion and repeat the WBRT-SIB planning. Resubmission of the new treatment plan with revised contours does not require review to occur prior to WBRT-SIB initiation UNLESS requested by the Principal Investigator. This determination will be made at the time that unacceptable deviations are communicated to the treating physician.

7.1.7. Critical Structure Constraints

Table 7-2. Critical Structure Constraints

Structure	Dose constraint	
Optic nerves and chiasm	D_{max}	34 Gy
Cochlea	D_{max}	32 Gy
Pituitary	D_{max}	36 Gy
Brainstem	D_{max} < 5 cc	44 Gy > 37.5 Gy

*Assuming α/β ratio of 2 for CNS normal structures and highest dose per fraction scenario (i.e., 8 fractions).

7.1.8. Use of Neuroprotective Agents

Memantine and other similar neuroprotective agents should not be used with patients on this trial.

7.1.9. Radiation Therapy Interruptions

1. Radiotherapy will be continued without interruption if at all possible.
2. If the sum total of radiotherapy interruptions exceeds 3 normally scheduled treatment days, the treatment will be considered an unacceptable deviation from the protocol. This should be reported to the Principal Investigator and the patient will be considered inevaluable on final data analysis.

7.2. Neurocognitive Function Assessment

Neurocognitive function assessment will be performed using the HVLT-R Neurocognitive assessment will be performed on all patients during a clinic visit at baseline (i.e., before first treatment, at the time of simulation if possible) and 3, 6, and 12 months after treatment ends.

7.2.1. HVLT-R

The HVLT-R is a 12 noun list with 4 words each from 1 or 3 semantic categories that are learned over the course of three learning trials. After 20-25 minutes, delayed recall and recognition are also assessed. This test is estimated to take 5-10 minutes with a 25 minute delay in the middle to allow for appropriate assessment of delayed recall. The focus of this test is on assessing verbal learning and memory. Please see Appendix 4 for a sample of one of the forms for the HVLT-R. The forms used for study will need to be purchased. This test may be administered remotely per the discretion of the PI.

7.3. Quality of Life Assessment

7.3.1. FACT-Br

FACT-Br is a self-administered questionnaire assessing multiple dimensions of a person's daily life, including physical, social, emotional, and functional well-being, as well as specific questions related to neurocognitive quality of life that might be affected by cancer therapy to the brain. A total of 50 questions arranged on 3 pages are present, all using a 5-point Likert scale. The FACT-Br is estimated to take 5 minutes to complete.

Participants will be given the FACT-Br to complete either on paper, computer, or tablet either during a clinic visit or completed at home, at baseline (i.e., before first treatment, at simulation if possible) and 3, 6, and 12 months after treatment ends. Please see Appendix 5 for a copy of the FACT-Br.

7.4. Tumor Assessment

Standard diagnostic quality MRIs will be ordered for routine follow-up at 3, 6, and 12 months after treatment ends. Please see Appendix 3 for details regarding the Response Assessment in Neuro-Oncology Brain Metastases (RANO-BM) criteria. We plan on adhering to the RANO-BM guidelines except in the following situations:

1. RANO-BM specifies that no more than 5 "target lesions" are followed for the study outcome. Further, it cautions on following lesions > 5 mm but < 10 mm in maximal dimension, but does provide guidelines for this situation. We plan on following all (i.e., potentially > 5) lesions that are treated and > 5 mm in maximal dimension for the study outcome using the RANO-BM suggested criteria for lesions < 10 mm in maximal dimension.
2. We also plan on following treated lesions < 5 mm in size for descriptive assessment as per RANO-BM guidelines. In particular, we agree that it is difficult to reliably reproduce small measurements (i.e., measurements for partial response or slight progression) with such small sizes and the limitation of MRI slice thicknesses. However, as these are treated lesions, we would still like to follow them prospectively.

7.5. Correlative Blood and Urine Collection

Blood and urine will be obtained from patients who consent to this optional procedure at the following time points: at baseline (i.e., before first treatment, at simulation if possible), 1st day of radiation treatment (before and after treatment delivery), 5th day of radiation treatment (after treatment delivery), last day of radiation treatment (after treatment delivery), and at the 1-month follow-up visit. One 10 mL tube of blood and approximately one cup of urine (~ 100 mL) will be collected at each time point. Blood and urine will be delivered to the laboratory of [name] in the IU Department of Radiation Oncology for processing and analysis.

8. STUDY CALENDAR

	Prior to treatment		Treatment	Post WBRT-SIB treatment follow up			
	Within 30 days prior registration	Within 2 weeks prior to treatment start		WBRT-SIB	1 month +/-14 days	3 months +/-30 days	6 months +/-30 days
REQUIRED ASSESSMENTS							
History and physical	X						
Karnofsky Performance Status evaluation	X			X	X	X	X
GFR/ Cr Cl	X						
Serum pregnancy test (if applicable)		X					
Adverse events		X ²	X ²	X	X	X	X
Neurocognitive function assessment		X			X	X	X
Quality of life assessment		X			X	X	X
DISEASE ASSESSMENT							
Contrast-enhanced brain MRI	X						
CT simulation scan		X					
TREATMENT							
WBRT-SIB planning and approval		X					
WBRT-SIB treatment			X				
CORRELATIVE STUDIES							
Optional blood and urine collection ¹		X	X	X			
FOLLOW-UP							
Physical exam and neurologic assessment				X	X	X	X

Footnotes:

1. Time points for correlative blood and urine collection: at time of simulation, 1st day of radiation treatment (before and after treatment delivery), 5th day of radiation treatment (after treatment delivery), last day of radiation treatment (after treatment delivery), and at the 1 month follow-up visit.
2. Adverse events related to blood draw and urine collection only will be documented at these time points.

9. CRITERIA FOR REMOVAL FROM THE STUDY

Every subject should be encouraged to remain in the study. Possible reasons for early withdrawal may include, but are not limited to, the following:

1. Withdrawal of consent – Subject decides to withdraw from the study. This decision must be an “independent decision” that is documented in the source documentation.
2. Principal Investigator and/or treating physician discretion – The Principal Investigator and/or treating physician may choose to withdraw a subject from the study if there are safety (or other) concerns.
3. Subject becomes pregnant.
4. Subject non-compliance.
5. Subject lost to follow-up.
6. Subject death.

10. STATISTICAL METHODS

10.1. General Considerations

Statistical analysis of this study will be the responsibility of the Department of Biostatistics at Indiana University School of Medicine. Parameter estimates and relevant summary statistics will be reported for both efficacy and safety outcomes. Continuous variables will be summarized by means, medians, minima, maxima and standard deviations. Categorical variables will be summarized by frequencies and percentages. Missing data will not be imputed. Additional exploratory analysis will be conducted when appropriate. Changes from the analysis plan will not require an amendment to the protocol unless it changes a significant feature in the protocol. The statistical analysis methods are outline below.

10.2. Study Design

This is a Pilot, Phase 2, sequential two-cohort trial. No randomization or blinding will be done.

10.3. Criteria for Stopping Study

An interim analysis is planned when the final patient in Cohort A finishes their six month assessment. If 20% or more of the evaluable subjects have in-brain distant failure at the 6 month time point, then the study will stop.

Additionally, there will be an early stopping rule in place. Each patient will be evaluated at 6 months for in-brain distant failure. If 4 patients out of the first 10 patients within each cohort have in-brain distant failure at 6 months, then the expected percent of patients would be double of what is expected (40% vs the expected 20%). This finding will prompt a re-assessment of treatment efficacy to determine if the cohort should continue.

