3. OUTCOME MEASURES

3.1. Primary Outcome Measure

In-brain distant failure, defined as an actuarial 6-month rate of new parenchymal lesions seen outside the planning target volume of any lesion that received SIB on any post-treatment MRI (in all 3 planes) by 6 months. Follow-up MRIs will be fused with the planning scan using our planning software for this assessment.

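### The early check in 10.3 counts failures 'at 6 months' while the endpoint counts them on any MRI by 6 months, so it can act one to two months later than it needs to and may miss a failure followed by death (minor)

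*Combined protocol and SAP*

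**What the plan says.** Section 10.3 (Criteria for Stopping Study) contains two rules.

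- The early rule states: "Each patient will be evaluated at 6 months for in-brain distant failure". It is met "If 4 patients out of the first 10 patients within each cohort have in-brain distant failure at 6 months". The consequence is a review, not a stop: "This finding will prompt a re-assessment of treatment efficacy to determine if the cohort should continue". No accrual pause is stated.
- The interim rule, applied once the last Cohort A patient has had the six-month assessment, stops the study if 20% or more of evaluable subjects "have in-brain distant failure at the 6 month time point".

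Section 3.1 (Primary Outcome Measure) defines the event differently in time, as a new parenchymal lesion outside the boosted volumes "on any post-treatment MRI (in all 3 planes) by 6 months". Section 7.4 (Tumor Assessment) sets the scans: "Standard diagnostic quality MRIs will be ordered for routine follow-up at 3, 6, and 12 months after treatment ends".

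Two other sections bear on patients who die early. Section 10.4.3 limits the efficacy population to patients evaluated on the 6-month scan. Section 10.5 replaces patients who die before 6 months only if they had no confirmed in-brain distant failure. Section 10.5 also sets 20 evaluable and up to 25 enrolled per cohort, and gives limiting exposure to the reduced dose as a reason for the sample size.

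**The concern.** Under 3.1 a new lesion on the 3-month MRI is already an endpoint event, and later scans cannot undo it. Section 10.3 nevertheless ties both the evaluation and the count to 6 months, and does not say that the check runs when the fourth failure is documented. Two consequences follow from a literal reading.

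1. **Timing.** Four failures seen at 3 months need not trigger the review until those patients reach 6 months. Enrolment may continue meanwhile, although the information that the rule needs already exists.
2. **Completeness.** A patient with a new lesion at 3 months who dies before the 6-month scan could be left out of the count. Section 10.5 implies that this patient should count, since only deaths without confirmed failure are replaced. Section 10.4.3 points the other way. Missing such patients would make the rule less sensitive than the 4-of-10 threshold suggests.

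At stake is how many patients enter a cohort before a review that the plan itself wants. In Cohort A, four failures among 20 evaluable patients also meet the interim stopping criterion (4/20 = 20%), so at that size later patients could not reverse the decision. With 25 evaluable they could (4/25 = 16%).

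**Working it through.** **The plan's own figure.** 4/10 = 40%, twice the expected 20%, as 10.3 states. It reproduces.

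**Trigger probability.** P(X ≥ 4) for X ~ Binomial(10, p) is 0.121 at p = 0.20 and 0.618 at p = 0.40. If every failure by 6 months is eventually counted, the date of counting does not change these values: the ten patients and the threshold are the same.

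**Inputs for the timing**

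- From the documents: scans at 3 and 6 months after treatment ends (7.4); 8 or 10 daily fractions at five a week, taken as 0.5 month of treatment (7.1.1); at most 25 enrolled per cohort (10.5); trigger at 4 of the first 10 (10.3).
- Assumed: Poisson accrual at 0.5, 1, 2 or 3 patients a month; a true 6-month failure rate of 40%; exponential failure times; no deaths. The exponential model puts 1 − √0.6 = 0.225 of patients in failure by 3 months, which is 0.225/0.40 = 56% of the 6-month failures.

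**Three ways of timing the trigger**, among simulated cohorts with at least 4 failures in the first 10 (40,000 cohorts simulated per accrual rate):

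- A: wait until patient 10 has the 6-month scan.
- B: count each failure at that patient's own 6-month visit, and trigger at the fourth.
- C: count each failure on the scan that shows it (3 or 6 months), and trigger at the fourth.

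| Accrual per month | Mean enrolled at trigger: A / B / C | Months C precedes B | Fewer enrolled, C vs B | Months C precedes A |
|---|---|---|---|---|
| 0.5 | 13.3 / 10.8 / 10.0 | 1.6 | 0.8 | 6.5 |
| 1 | 16.5 / 14.1 / 12.6 | 1.5 | 1.5 | 4.0 |
| 2 | 22.3 / 20.3 / 17.7 | 1.3 | 2.5 | 2.6 |
| 3 | 24.7 / 24.0 / 21.8 | 1.2 | 2.2 | 2.0 |

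**Sensitivity.** Dropping the exponential assumption, letting 30% to 70% of failures be visible at 3 months, and taking a true rate of 20% or 40%, C precedes B by about 0.4 to 2.0 months over the same accrual range. The gain is positive throughout.

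**Deaths.** The simulation has none. If some failures are followed by death before 6 months and a literal count drops them, the current trigger probabilities lie below 12.1% and 61.8%. Counting those patients brings the probabilities back to these values. The documents do not allow the shortfall to be sized.

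**The case against.** **'At 6 months' may simply be shorthand for 'by 6 months'.** Section 2.1 uses the former phrase for the same endpoint. This is plausible. If it is the intent, the edit only writes it down, but the text still does not say when the count is made.

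**A reader might infer that the check waits for the tenth patient's 6-month scan**, and so claim a gain of 4.0, 2.6 or 2.0 months at 1, 2 or 3 patients a month. The text does not require this. It evaluates each patient individually, so four failures at their own 6-month visits satisfy the rule before patient 10 is complete. Comparison B is the fair one, and the column for A is an upper reading.

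**A reader might infer that the check will come when the cohort is nearly full.** The documents give no accrual rate. Under B, mean enrolment at the trigger is about 11 of 25 at 0.5 a month and 24 of 25 at 3 a month. The statement is conditional.

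**A reader might infer that error rates cannot change.** That holds only if no failure is currently lost through death. If some are, the trigger probability rises to its intended level.

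**Other oversight exists.** Section 13 requires monthly review with summaries to the monitoring committee, and 13.2 allows early closure at any time. Nothing prevents action on four failures seen at 3 months, and this softens the harm. Neither provision carries a failure count, so neither replaces the rule.

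**The death gap is partly answered** by the replacement wording in 10.5. That stands, but 10.4.3 conflicts with it and 10.3 does not settle which applies.

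**Conclusion.** The mismatch between 10.3 and 3.1 is real, and correcting it is worth two sentences. Followed literally, 10.3 can hold back a re-assessment whose information already exists, and can overlook a failure followed by death.

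At a true 40% failure rate with exponential failure, the delay averages about 1.2 to 1.6 months, and 0.8 to 2.5 more patients are enrolled, over an assumed accrual of 0.5 to 3 a month. These figures rest on that accrual range and on the share of failures visible at 3 months.

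Severity is minor. The trigger is a re-assessment, general monitoring exists, and at 3 patients a month about 22 of 25 are already enrolled even when the check acts at the fourth documented failure.

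**What to change.** Make these changes in 10.3.

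1. Define the count by reference to 3.1: a failure is a qualifying new lesion on any post-treatment MRI up to and including the 6-month visit, and it counts whether or not the patient later dies or misses the 6-month scan.
2. State the timing: the re-assessment is held as soon as the fourth such failure is documented among the first 10 patients treated in a cohort. Keep the 4-of-10 threshold.
3. In the interim rule, replace the wording tied to the 6-month time point with 'by 6 months'.

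The cost is a short text edit. It needs no extra patients or scans and no change of threshold. Without deaths the trigger probability stays at 12% (true 20%) and 62% (true 40%). Where failures followed by death were being missed, it rises to those levels. The edit limits exposure only partly if accrual is fast.

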10.4. Analysis Datasets

10.4.1. Enrolled Population

The enrolled population comprises all subjects who meet the eligibility criteria and are registered onto the study.

10.4.2. Safety Population

The safety population comprises all subjects who have received at least one dose of radiation. This set will be used for safety analysis.

10.4.3. Efficacy Population

The efficacy population comprises all subjects who have received at least one dose of radiation, and have been evaluated for the primary endpoint (the 6 month scan). This population will be used for efficacy analysis.

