To assess neurocognitive function, we will use the Hopkins Verbal Learning Test Revised (HVLT-R.) The HVLT-R has been used and validated in multiple trials related to brain metastasis. In particular, RTOG 00-18 was a feasibility study of neurocognitive function testing on a national scale[40]. They demonstrated compliance rate for testing before treatment, at treatment completion, and at 1 month was $\geq 95\%$, $\geq 84\%$, and $\geq 70\%$, respectively. Several tests were assessed, including the HVLT. Meyer et al. reported on a phase III randomized trial investigating the benefit of motexafin gadolinium on the survival and neurologic and neurocognitive outcomes of patients receiving WBRT for brain metastases[41]. Of the several neurocognitive tools used, the HVLT for immediate recall, delayed recall, and recognition were incorporated. This study did not demonstrate any difference in time to neurocognitive function. It did show that compliance with testing was 87-98% at baseline and 77-87% at 6 months.

For the present protocol, we will be using the HVLT-R. The HVLT-R is a 12 noun list with 4 words each from 1 or 3 semantic categories that are learned over the course of three learning trials. After 20-25 minutes, delayed recall and recognition are also assessed. This test is estimated to take 5-10 minutes with a 25 minute delay in the middle to allow for appropriate assessment of delayed recall. The focus of this test is on assessing verbal learning and memory. In situations where in-person visits are discouraged or not allowed (e.g. the COVID-10/SARS-Co-V2 pandemic), we may opt to administer the HVLT-R via a telehealth visit.

A baseline neurocognitive function assessment will be performed at the time of CT simulation. The follow-up time points chosen include 3-, 6-, and 12-months post-treatment. Patients will be seen at 1-month post-treatment as well but will not be assessed for neurocognitive function at that time. Given our inclusion/exclusion criteria of a life expectancy of at least 6 months per ds-GPA (see Appendix 1 for more detail), we anticipate that a large proportion of our patients will be assessed at time points up to 6 months. We acknowledge the possibility that a small but significant proportion of our patients may die before the 12-month assessment but remain interested in attempting to examine long-term

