3.2. Secondary Outcome Measures

1. Treated lesion control, defined as an actuarial 6-month rate of any new, recurrent, or progressing (as defined by RANO criteria, see Appendix 3) tumor within the planning target volume on any post-treatment MRI by 6 months. Follow-up MRIs will be fused with the planning scan for this assessment.
2. Overall survival, defined as an actuarial 6-month rate of patients still alive regardless of disease status at 6 months.
3. Neurocognitive function change, defined as the change from baseline neurocognitive testing scores at a 6-month time point with respect to the HVLT-R.
4. Health-related quality of life change, defined as the change from baseline quality of life assessment at a 6-month time point with respect to the FACT-Br tool.
5. Performance status change, defined as the change from baseline performance status at a 6-month time point with respect to the KPS clinical assessment tool.
6. Incidence of early and late adverse effects as defined by the CTCAE, at any time point during the study follow-up.

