10.5. Sample Size

A total sample size of 20 evaluable subjects per cohort was determined to balance the competing goals of assessing the primary objective while not exposing more subjects to an investigational decreased radiation procedure than is required. Historical data has shown that approximately 20% of subjects with standard radiation treatment show in-brain distant failure at 6 months. This trial is looking to see if decreased radiation will provide similar efficacy to the standard of care. There will be an interim analysis after the first cohort completes their 6 month scans. If less than 20% of the subjects have in-brain distant failure, then the second cohort will start.

With 20 evaluable subjects in a cohort, the 90% confidence interval around the proportion of subjects who are expected to have in-brain distant failure at 6 months would extend at most +/- 14.7%. Up to 25 subjects may be enrolled in each cohort. Although subjects who die before 6 months without confirmed in-brain distant failure would be replaced if possible, the following table will show the estimated confidence interval widths assuming the 20% proportion of subjects who may have in-brain distant failure at 6 months:

Number of Patients:	15	20	25
90% Confidence interval width:	17.0%	14.7%	13.2%

As stated in section 7.1.9, patients will not be considered evaluable if the sum total of radiotherapy interruptions exceeds 3 normally scheduled treatment days.

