10.9. Analysis of Secondary Objectives

For Local Control and Overall Survival, the median and the corresponding two-sided 95% confidence intervals will be calculated using the Kaplan-Meier method. Estimates and 95% confidence intervals will also be provided for 6 and 12 months.

For quality of life measures and neurocognitive assessments, appropriate subscales will be calculated at each time point, along with change from baseline to 3, 6, and 12 months, and summarized descriptively by cohort. Baseline Karnofsky Performance Status and change from baseline to 1, 3, 6, and 12 months will also be summarized and reported by cohort. Summary descriptive statistics only (i.e. no inferential statistics) will be used for all measures except for HVLT-R. An analysis will be done for HVLT-R to use the change from baseline results and compare them to the results generated from the RTOG 0933 study. Wilcoxon Rank Sum Tests will be used for this comparison.

All safety data will be listed. For the treatment-emergent AEs, namely AEs started or worsened during the on-treatment period, the incidence will be summarized by system organ class and/or preferred term, severity based on CTCAE grades, type of adverse event and the relation to the study drug. Deaths reportable as SAEs and non-fatal serious adverse events will be listed by and tabulated by type of adverse event. This will be done with the safety set.

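### Limiting efficacy analysis to patients with a 6-month scan makes 6-month overall survival about 100% whatever happens, and conflicts with sections 3.1 and 10.5 on patients who fail and then die

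*Combined protocol and SAP*

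**What the plan says.** **Populations.** To enter the efficacy population (10.4.3) a patient must have had at least one dose of radiation and must "have been evaluated for the primary endpoint (the 6 month scan). This population will be used for efficacy analysis". The safety population (10.4.2) is all treated patients, and "This set will be used for safety analysis". The enrolled population (10.4.1) is given no analysis. Section 10.1 recognises only efficacy and safety outcomes.

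**Survival and lesion control.** Section 3.2 lists "Overall survival, defined as an actuarial 6-month rate of patients still alive regardless of disease status at 6 months". Section 10.9 states: "For Local Control and Overall Survival, the median and the corresponding two-sided 95% confidence intervals will be calculated using the Kaplan-Meier method", and adds estimates at 6 and 12 months. It names the safety set for the safety data but no set for survival or local control.

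**Primary endpoint.** Section 3.1 counts a new lesion outside the boosted volumes on any MRI after treatment up to 6 months, and 7.4 schedules MRIs at 3 and 6 months. Section 10.5 says that "subjects who die before 6 months without confirmed in-brain distant failure would be replaced if possible", which implies that a patient who fails first and then dies is kept.

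**Numbers and decision rule.** Section 10.5 sets "A total sample size of 20 evaluable subjects per cohort" and adds: "Up to 25 subjects may be enrolled in each cohort". Under 10.3 the study stops if 20% or more of evaluable subjects have distant failure. Sections 10.5 and 10.11 repeat the threshold without the word evaluable. Apart from the exclusion for long treatment interruptions (7.1.9, 10.5), no section defines that word.

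**The concern.** A patient who had the 6-month scan was alive at about 6 months. If only such patients are analysed, a 6-month survival rate carries almost no information. Kaplan-Meier cannot repair this, because the early deaths never enter the dataset. Median and 12-month survival become estimates conditional on surviving to the scan. Treated-lesion control suffers in the same way: a progression seen on the 3-month MRI disappears if the patient dies before the next scan.

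The plan expects early deaths. Section 10.5 makes provision for patients who die before 6 months. Section 1.4 says only that "we anticipate that a large proportion of our patients will be assessed at time points up to 6 months"; this is weaker support, since the deaths it goes on to mention are those before 12 months.

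The second problem is smaller but touches the decision to open Cohort B. Read literally, the parenthesis in 10.4.3 drops a patient whose distant failure was seen at 3 months and who died before the 6-month scan. Sections 3.1 and 10.5 count that patient. With a hard 20% cut and 20 patients, one classification can reverse the decision.

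**Working it through.** **1. The plan's own figure.** No survival figure is stated. The only computed figure that rests on the evaluable set is the 90% half-width in 10.5, at an assumed 20% failure rate: 1.645 × √(0.2 × 0.8 / n) = 17.0%, 14.7% and 13.2% for n = 15, 20 and 25. All three reproduce.

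**2. Survival from the plan's enrolment numbers, with no survival model.** Suppose 25 are treated and 5 die before the scan. All treated: 20/25 = 80%, exact 95% CI 59.3-93.2%. The 10.4.3 set: 20/20 = 100%.

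**3. Survival using Table 16-2 (illustration).** Eighteen groups have a median of at least 6 months (6.9 to 46.8), so 4.2 does not exclude them. The protocol says the web version governs, so the printed table only illustrates. Assuming exponential survival, S(t) = 0.5^(t/median):

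- S(6) = 0.547 at median 6.9, 0.726 at 13.0 (the middle of the 18) and 0.915 at 46.8.
- The unweighted mean over the 18 groups is 0.704, so 25 × (1 − 0.704) = 7.4 deaths per 25. Fifteen of the 18 groups lie below 0.80.
- The 10.4.3 set shows 100% if scans fall at 6 months or later. If every scan falls at the earliest date in the ±30-day window (5 months), it shows S(6)/S(5) = 0.904 to 0.985.
- At median 13.0, true 12-month survival is 0.527. The 10.4.3 set shows S(12)/S(5) = 0.689 to S(12)/S(6) = 0.726.

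**4. Lesion control (assumed counts).** Of 25 treated, 5 die between the two scans, 2 of them with progression in the treated volume at 3 months; 2 of the 20 survivors progress at 6 months. All treated, Kaplan-Meier: (23/25) × (18/20) = 82.8%. The 10.4.3 set: 18/20 = 90%.

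**5. The Cohort B decision (assumed counts).** Take 20 patients evaluable under 3.1 and 10.5, with 4 failures, one of whom died after a 3-month failure.

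- 3.1/10.5: 4/20 = 20%, stop.
- 10.4.3 read literally: 3/19 = 15.8%, go.
- If that patient is replaced: 3/20 = 15% (go) when the replacement does not fail, 4/20 = 20% (stop) when it does.

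**6. How often the two readings disagree (simulation).** 200,000 cohorts of 25 patients in order, the first 20 evaluable used, scans at 3 and 6 months, exponential failure times with 20% failing by 6 months, exponential death times. The doubled death hazard after failure is an assumption.

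| Median survival (months) | Rate, literal 10.4.3 / 3.1-10.5, independent death | Opposite decisions | Rate, literal 10.4.3 / 3.1-10.5, hazard doubled after failure | Opposite decisions |
|---|---|---|---|---|
| 6.9 | 0.200 / 0.228 | 10.4% | 0.156 / 0.203 | 17.4% |
| 9.2 | 0.200 / 0.221 | 8.3% | 0.167 / 0.203 | 14.4% |
| 13.0 | 0.200 / 0.214 | 6.5% | 0.175 / 0.201 | 11.8% |
| 15.2 | 0.200 / 0.212 | 5.8% | 0.179 / 0.201 | 10.6% |
| 46.8 | 0.200 / 0.204 | 1.6% | 0.193 / 0.200 | 3.3% |

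Every disagreement was go under 10.4.3 and stop under 3.1/10.5; the reverse was 0.0% throughout.

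**The case against.** Five points can be made for the plan.

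- **Intent.** Section 10.9 names no population for survival, and an actuarial 6-month rate would be pointless if everyone analysed had to reach the scan. The authors may well have meant all treated patients. Section 5 also lists survival separately from efficacy outcomes. That list describes a future trial, however, and no section assigns survival here to any other set. An unintended default is plausible, but the written rule still gives the wrong result.
- **Importance.** Survival and lesion control are secondary and estimation-only, with no threshold attached. Early deaths would also appear in the disposition summary (10.7), since death is a listed reason for leaving the study (section 9). This limits the harm, but a listing of deaths does not correct a reported survival rate of about 100%.
- **Primary endpoint.** Being evaluated for the endpoint can be read through 3.1, so that a 3-month failure suffices. Sections 3.1 and 10.5 do point that way, and only the parenthesis disagrees. On its own this part is a lesser matter of clarification.
- **Size of the illustrations.** The 10.4% and 17.4% figures put every patient in the worst admissible group, where only about 25 × 0.547 = 13.7 patients (independent death) would reach the 6-month scan. They also fix the failure rate at the threshold. With independent death, disagreement is 0.8-5.0% at a 10% failure rate and 0.9-7.8% at 30%. The 80% example attributes all five extra enrolments to death, although interruptions and missed scans also use them. The unweighted 70% is not a case-mix forecast. These are fair limits on size, not on the finding.
- **Bias.** If death is independent of failure, the literal 10.4.3 rate is unbiased (0.200) and the 3.1/10.5 rate runs high. This stands, and the fix below states it.

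**Conclusion.** The concern holds: the stated rule is wrong as written. Applied literally, 10.4.3 gives 6-month survival of about 100%, or 90.4-98.5% if every scan falls at 5 months. Under exponential survival with the Table 16-2 medians, the figure in all treated patients would be 54.7-91.5%. The contrast of 80% with 100% needs no survival model, only that the five extra patients die before the scan. Later survival and lesion control are also made to look better than they are.

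The conflict over failure followed by death is the smaller part. At a 20% failure rate it changes the Cohort B decision in 1.6-10.4% of cohorts if death is independent of failure, and in 3.3-17.4% under the assumed doubling of hazard. The change is always towards opening the lower-dose cohort.

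The first part is what makes correction necessary, because a stated secondary endpoint would otherwise be nearly uninformative.

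**What to change.** 1. In 10.4.3 and 10.9, analyse overall survival and treated-lesion control in all patients who received at least one fraction, including those who die before the 6-month scan.
2. Reconcile 10.4.3 with 3.1 and 10.5 by defining evaluable as having a 6-month scan, or a distant failure confirmed on an earlier MRI after treatment. Leave the interruption exclusion in 7.1.9 and 10.5 unchanged. Use the defined term in 10.3, 10.5, 10.8 and 10.11.
3. Keep the proportion among evaluable patients (10.3) as the decision statistic, and report beside it the actuarial 6-month rate that 3.1 defines, in all treated patients. Say plainly that the evaluable proportion can run high, because only failure-free deaths leave its denominator: 20.4-22.8% when the true rate is 20% and death is independent of failure.

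**Cost.** Wording in six sections (10.3, 10.4.3, 10.5, 10.8, 10.9 and 10.11) and one added estimate, with no new visits or patients. Reported survival, and possibly the failure rate, will look less favourable.
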